1.3 SAMPLE SIZE RATIONALE

The sample size is based on experience from the VTI-208 study.

The VTL-308 inclusion criteria have been established to reflect a subset of the VTI-208 population, i.e. the VTI-208 population with baseline criteria of MELD <30, age <50, INR \leq 2.5, creatinine <1.3 mg/dL and serum total bilirubin \geq 16 mg/dL.

The key design feature of the VTL-308 Protocol is that the primary analysis of treatment effect on overall survival is based on a log-rank statistic having two-sided significance level of 0.05. This primary analysis will be performed when the last of 150 randomized subjects has been followed for at least 91 days. Sample size adjustments may be made only in the instance in which more than 150 randomized subjects would be needed in order to achieve the minimum threshold of 55 deaths at the time of that analysis.

When the study is nearing completion of enrollment, the total number of deaths occurring through that time will be calculated, along with the mortality rate, based on the enrollment rate per month and the time to death. Based on these calculations a projection will be made of the total number of subjects that will need to be enrolled to achieve the minimum threshold of 55 deaths at the time of study data lock (estimated to be approximately 5 months after last patient enrolled). The total sample size may then be adjusted accordingly.

Analysis of the VTI-208 data suggests that in a group of subjects meeting the inclusion criteria for VTL-308, it might be reasonably anticipated that one-year survival will be in the range from 40% to 48% in the Control group. Under the assumption of a proportional hazards model, if the hazard ratio is 0.4 in favor of the ELAD group, this leads to the anticipation that one-year survival will be in the range from 69.5% to 74.5% in the ELAD subjects.

The rationale for the sample size is based on the following assumptions:

- the analysis of the primary endpoint of overall survival will be conducted in the ITT population;
- the prospectively defined population behaves similarly to the corresponding subgroup of the VTI-208 study;
- the log-rank test will be used to compare two survival curves using a two-sided significance level of 0.05;
- one-year survival will be in the range from 40% to 48% in the Control group and in the range from 69.5% to 74.5% in the ELAD group;
- the accrual distribution will be uniform with an accrual time that will be at least 720 days;

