- the rate of missing data will be in the range from 0% to 10%; and
- the primary analysis will be the time when at least 55 deaths have occurred and the time when the last enrolled subject has been followed for at least 91 days. It follows that a sample size for the VTL-308 trial of 75 subjects per group with 1:1 allocation would provide a number of events (i.e., deaths) in the range from 55 to 65, even if we assume average follow-up of only 1 year. With 55 events, the trial will have 90% power if the true hazard ratio is 0.417; with 65 events, the trial will have 90% power if the true hazard ratio is 0.447.

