7.2 SECONDARY EFFICACY ANALYSIS

7.2.1 Proportion of Survivors at Study Days 28 and 91

The effect of ELAD on the proportion of subjects who survived at End of Study Days 28 and 91 will be estimated with 95% confidence intervals for the ITT, mITT, PP and Safety population. Analyses will be presented using the last date known alive, leaving subjects who are not known to be dead, in both the numerator and the denominator. Additional analysis will be done for subjects whose Study Day 28 and/or 91 survival status is unknown at the time of database lock. These subjects will not be included in either the numerator or the denominator of the calculation.

7.2.2 Early Change in Bilirubin Level (ECBL) at Study Day 7

There is a strong correlation between ECBL and response to therapy, as demonstrated by the prior studies evaluating the effects of corticosteroids in AH (Mathurin et al. 2003). Post-hoc analysis of the VTI-208 Safety population suggested that there were more ECBL20 Yes subjects in the ELAD-treated group, and the survival of ECBL20 Yes subjects was significantly higher than the survival in ECBL20 No subjects.

A secondary endpoint for the VTL-308 study will be the proportion of subjects who achieve ECBL20 at Study Day 7 in the ITT population. The 20% or greater threshold for the reduction in ECBL, and the 7-day time point, were chosen as this is consistent with prior literature (Lee et al. 2014, Li et al. 2016, López-Velázquez et al. 2014, Louvet et al. 2007, Mathurin et al. 2003, Morris and Forrest 2005) and in the findings from the VTI-208 study. Differences between treatment groups will be analyzed using a Chi-squared test. The same analysis will also be carried out on the safety population as an exploratory sensitivity analysis.

Definition of Early Change in (total) Bilirubin (tBili) Level (ECBL)

Subjects who died within 7 days (including Day 7) will be excluded from the analysis. ECBL (End point minus start point) will be expressed as a percentage of start point.

- For the start point value, “Within 6 hours prior to ELAD start” tBili value and “Day 2” tBili value will be used for ELAD-treated subjects and Control subjects, respectively;

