7.3.3 Outcome Relative to Selected Screening Factors

In addition, exploratory analyses of outcome relative to selected screening factors will be conducted. The overall survival rates at Study Day 28 and Study Day 91 for the ELAD treatment group and the Control group will be provided for the following subgroups:

- Steroid / pentoxifylline / NAC use at Randomization (Yes/No);
- Steroid / pentoxifylline / NAC use during treatment period (Yes/No);
- Steroid / pentoxifylline / NAC use after treatment (Yes/No).

For the ELAD subjects, treatment period is defined as the period from initiation of ELAD treatment to ELAD treatment stopping. For the Control subjects, treatment period is defined as the period from Study Day 2 to Day 7.

7.3.4 Early Change Bilirubin at Different Levels at Study Day 7

In order to further explore the change in bilirubin as a potential surrogate endpoint for studies of new therapeutic approaches to the treatment of sAH, together with findings from VTI-208 that significant differences were observed for all ECBL values between ECBL 10% and ECBL 40% in the Safety population in the VTI-208 study (VTL data on file), additional exploratory analyses will be carried out. The proportion of subjects will be presented by treatment group and by the following bilirubin categories for the Safety and ITT Populations. Differences between treatment groups at each cutoff will be evaluated using a Chi-squared test.

- 0% reduction from baseline in bilirubin (ECBL0);
- 10% reduction from baseline in bilirubin; (ECBL10);
- 15% reduction from baseline in bilirubin; (ECBL15);
- 25% reduction from baseline in bilirubin. (ECBL25);
- 30% reduction from baseline in bilirubin. (ECBL30);
- ECBL as a continuous variable (use median as cutoff).

Furthermore, exploratory analyses will be carried out and the proportion of survivors at Study Days 28 and 91 will be presented by achieving bilirubin reduction (Yes vs No for ECBL0, ECBL10, ECBL15, ECBL20, ECBL25, ECBL30) for overall, ELAD treatment group and Control group using the ITT Population.

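### SAP 7.3.4 labels an ECBL item continuous but analyses it as a median split, so ECBL is never compared between groups on its measured scale

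*SAP*

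**What the plan says.** SAP 7.2.2 defines ECBL on a percentage scale: "ECBL (End point minus start point) will be expressed as a percentage of start point". The start point is the value within 6 hours before ELAD start, or Day 2 in Control. The end point is Day 7, with a rule that substitutes the 24-hour post-ELAD value when an ELAD subject's Day 7 sample was taken too close to the end of treatment. Early deaths are left out: "Subjects who died within 7 days (including Day 7) will be excluded from the analysis".

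The secondary endpoint is a fixed cut with literature cited for it: "A secondary endpoint for the VTL-308 study will be the proportion of subjects who achieve ECBL20 at Study Day 7 in the ITT population".

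SAP 7.3.4 sets out to explore bilirubin change as a possible surrogate. In ITT and Safety it lists cuts at 0, 10, 15, 25 and 30%, and then "ECBL as a continuous variable (use median as cutoff". For the whole list, "Differences between treatment groups at each cutoff will be evaluated using a Chi-squared test". The survival tables in the same section are split Yes/No at the fixed cuts only.

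**The concern.** The label and the method contradict each other. A programmer following the text would produce one more two-by-two table, at a cut that exists only in this sample. No source is cited for a median cut, unlike the 20% cut, and a sample median cannot be carried to another study. That sits badly with the section's stated interest in bilirubin change as an endpoint for future trials.

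Two things are at stake. The item yields a difference in proportions at an arbitrary point, with no estimate in percentage points of bilirubin change and no interval for one. And if ECBL is roughly normal, a median split uses only 2/π = 64% of the information that a t-test would use, asymptotically.

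**Working it through.** **1. Is ECBL analysed on its own scale anywhere?**

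| Place in SAP | Quantity | Start of change | Population | Between-group test |
|---|---|---|---|---|
| 7.2.2 | ECBL20 Yes/No | pre-ELAD / Day 2 | ITT (Safety as sensitivity) | chi-squared |
| 7.3.4 | cuts at 0, 10, 15, 25, 30% and the median | pre-ELAD / Day 2 | ITT, Safety | chi-squared |
| 7.3.6 | total bilirubin change by visit | randomization | ITT | baseline-adjusted MMRM |
| 8.5 | absolute and percent change by visit | pre-randomization baseline; also ELAD start / End of Study Day 2 | Safety | none |

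Section 7.3.6 is continuous but measures a different change and does not apply the ECBL end-point rule. It mentions extra summaries from ELAD start for selected analyses, but names no test for them. Section 8.5 covers the ECBL start points but rules out inference. So no row gives a continuous between-group comparison of ECBL as defined.

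**2. What does the median split cost?** The plan states no power, SD or effect size for ECBL, so there is no planned figure to reproduce.

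Inputs:
- From SAP 1.3: "a sample size for the VTL-308 trial of 75 subjects per group with 1:1 allocation". The exclusion of deaths through Day 7 will lower this by an unstated number.
- Alpha: SAP 1.3 says "the log-rank test will be used to compare two survival curves using a two-sided significance level of 0.05". None is given for ECBL, so 0.05 two-sided is assumed.
- Assumed: normal ECBL with equal SDs and a true shift d of 0.4, 0.5 or 0.6 SD.

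Formulas:
- Median split: p1 = Φ(d/2) and p2 = Φ(−d/2). Power = Φ{[(p1 − p2) − 1.96·√(0.5/n)] / √[(p1q1 + p2q2)/n]}, with q = 1 − p.
- t-test: noncentral t with noncentrality d·√(n/2) on 2n − 2 df.

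Example, d = 0.5 and n = 75:
- p1 = 0.599 and p2 = 0.401, so the difference is 0.197.
- The null term is 1.96 × √(0.5/75) = 0.160. The alternative SE is 0.080.
- (0.197 − 0.160)/0.080 ≈ 0.47, which gives 68.0% power.
- The t-test noncentrality is 0.5 × √37.5 = 3.06, which gives 86.0% power.

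Wilcoxon power needs simulation. Results at n = 75 per arm, normal data:

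| d | Median split, formula | Median split, simulated | Wilcoxon, simulated | t-test, exact | Loss vs Wilcoxon |
|---|---|---|---|---|---|
| 0.4 | 49.3% | 49.7% | 66.1% | 68.2% | 16.4 points |
| 0.5 | 68.0% | 67.6% | 84.1% | 86.0% | 16.5 points |
| 0.6 | 83.0% | 83.1% | 94.4% | 95.5% | 11.3 points |

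**3. Why quote 75 per arm?** A pooled-median split fixes both margins, so the test is discrete. Its exact null size, from the hypergeometric distribution, is 3.5% at 65 per arm, 6.6% at 72 and 5.0% at 75. Only at 75 do the two tests run at about the same alpha.

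**4. Does it depend on normality?** Yes. Simulated power at n = 75 and d = 0.4:

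| Errors | Median split | Wilcoxon | t-test |
|---|---|---|---|
| t with 3 df | 86.8% | 91.0% | 72.9% |
| Laplace | 86.4% | 83.5% | 69.6% |

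Wilcoxon gains about 4 points in the first case and gives up about 3 in the second.

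**The case against.** The strongest reply is that the plan already tests bilirubin change on a continuous scale. SAP 7.3.6 does so at every visit in ITT, adjusted for baseline, with an LOCF sensitivity analysis. SAP 8.5 adds percent change from the ECBL start points. This stands, and it defeats a reading that a reader might take from 7.3.4 alone: that the measured bilirubin scale goes unused and no mean difference will be available. What survives is narrower, namely that ECBL itself has no continuous comparison.

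Second, the item is exploratory and unpowered. SAP 7.3 allows further analyses, and median splits are common in the SAP's other exploratory work (7.1.2, 7.1.4, 7.3.2). That also stands, and it limits the consequence. But those sections present their splits as splits. SAP 7.1.3 lists several covariates as both continuous and dichotomized at the median. The 7.3.4 bullet may be shorthand for the same pairing, but no continuous test is named for it.

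Third, the power loss rests on assumptions that the documents do not supply. This is correct. A reader who varies the arm size from 65 to 75 might report a loss of 9 to 22 points. Those extremes come from 72 and 65 per arm, where the median split is respectively anti-conservative and conservative, so they mix lost power with unequal alpha.

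**Conclusion.** The inconsistency is on the face of SAP 7.3.4. The item is a data-dependent median split, and no planned analysis gives a treatment difference in ECBL, as SAP 7.2.2 defines it, on its measured scale with a confidence interval.

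The cost in power is about 11 to 17 points against Wilcoxon, given normal data, a shift of 0.4 to 0.6 SD, two-sided 0.05 and 75 per arm. It is conditional on all four. With heavy-tailed data it may be a few points either way.

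It would go too far to infer that the trial's efficacy conclusions are weakened. The primary log-rank analysis and the secondary ECBL20 endpoint do not depend on this item, and the 20% cut has its own cited support. This is a free improvement to an exploratory analysis.

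**What to change.** Replace the last bullet of the SAP 7.3.4 cutoff list with:

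> *ECBL as a continuous variable (percent change as defined in 7.2.2): Wilcoxon rank-sum test with Hodges-Lehmann difference and 95% CI, ITT and Safety populations.*

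Name it as the single lead analysis of this item, and keep ECBL20 as the secondary endpoint. If the median split is wanted as well, label it as one.

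If the team also wants to relate continuous ECBL to survival, time zero must be set at or after each subject's ECBL end-point measurement. A Cox model starting at Day 7 would be unsafe. SAP 7.2.2 lets an ELAD subject's end value be the 24-hour post-ELAD one, and Protocol 5.5.1 foresees delayed treatment with evaluations running beyond Day 7, so the covariate could be measured after follow-up has begun.

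The cost is one reworded bullet and one changed exploratory table, from data already collected.

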7.3.5 Lille Score

The Lille score ([Louvet et al. 2007](#)) is a composite score developed in order to help in the decision making about continued steroid administration to patients with sAH – i.e., a Maddrey Discriminant Function score of ≥ 32 . The score is measured over a 7-day period of therapy and

has been shown to have good prognostic value in predicting 90-day and 6-month survival. There are also data in the literature for measuring Lille after a 4-day period ([Garcia-Saenz-de-Sicilia et al. 2017](#)). Where the components for calculating the Lille score are available, the Lille score will be derived at Study Days 3, 4 and 7 (± 24 hours) as an exploratory composite biomarker.

The proportion of subjects who have Lille score <0.45 vs ≥ 0.45 at Study Days 3, 4 and 7 will be presented by treatment group for the ITT and Safety Populations. Differences between treatment groups will be analyzed based on a Chi-squared test. Additionally, the proportion of survivors at Study Day 28 and at Study Day 91 will be presented by treatment group and by the Lille score (<0.45 vs ≥ 0.45) at Study Days 3, 4 and 7 for the ITT Population. Lille scores at Study Days 3, 4, and 7 will be presented in a listing for the ITT and Safety Populations.

In order to avoid the effect of ELAD treatment on factors used in the calculation of Day 0 bilirubin for the Lille score, and to best align the 3, 4 or 7-day treatment period between the groups, baseline values will be taken immediately prior to the initiation of ELAD treatment for the ELAD treatment group, while the last evaluation prior to Randomization will be used for the Control group. For the post-baseline bilirubin, the measurement collected 24 hours after the last ELAD treatment is ended or the measurement at Study Days 3, 4 or 7, whichever is later, will be used for the ELAD treatment group, and the measurement at Study Days 3, 4 or 7 will be used for the respective Control group.

For both ELAD and Control groups, see [Section 0](#) for missing bilirubin values at Day 0 and applicable evaluation day (Study Days 3, 4 or 7). Use LOCF for missing albumin, creatinine and INR/PT at Day 0. If a lab test was not done before Randomization or initiation of ELAD treatment for Control or ELAD treatment groups, respectively, the first lab value after Randomization or initiation of ELAD treatment will be used. Subjects who die on or before the applicable evaluation day (Study Days 3, 4 or 7) will be excluded from the analysis.

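### SAP 7.3.5 compares Lille scores over unequal time windows: the ELAD Day 3 and Day 4 scores share one post-ELAD bilirubin from about Study Day 6 to 8, and at Day 7 the imbalance reverses

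*SAP*

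**What the plan says.** SAP 7.3.5 derives the Lille score at Study Days 3, 4 and 7, each with a window of 24 hours either side, "as an exploratory composite biomarker". The proportions below 0.45 and at or above 0.45 are compared between arms in the ITT and Safety populations: "Differences between treatment groups will be analyzed based on a Chi-squared test".

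The start points differ by arm. In the ELAD arm, "baseline values will be taken immediately prior to the initiation of ELAD treatment for the ELAD treatment group". The Control arm is anchored earlier: "while the last evaluation prior to Randomization will be used for the Control group". The end points differ too. For ELAD the choice lies between the 24-hour post-ELAD bilirubin and the nominal-day value: "whichever is later, will be used for the ELAD treatment group". Control has no such choice: "the measurement at Study Days 3, 4 or 7 will be used for the respective Control group". The stated reasons for the baseline choice are to keep ELAD's own effect out of the Day 0 values and "to best align the 3, 4 or 7-day treatment period between the groups".

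Other sections fix the timing. SAP 2 sets a 72-hour minimum and a 120-hour maximum for ELAD treatment. SAP 7.3.6 and SAP 8 treat End of Study Day 2 as the closest Control counterpart to ELAD initiation. For the secondary endpoint of early change in bilirubin (ECBL), SAP 7.2.2 pairs the pre-ELAD value with the Control Day 2 value. It takes Day 7 as the end point, or the 24-hour post-ELAD value when the Day 7 sample falls too close to the end of treatment.

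**The concern.** A Lille score depends on how far bilirubin has moved since baseline, so two arms can be compared only over similar intervals. Here the ELAD end point waits for treatment to finish and the Control end point does not. A subject who starts ELAD at about End of Study Day 2 is normally still on the circuit on Days 3 and 4, so no off-ELAD value exists on those days.

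At stake are the between-arm p-values at Days 3, 4 and 7. A difference at Day 3 or 4 could reflect extra elapsed days and would not be evidence of early response to ELAD. A difference at Day 7 could be distorted the other way.

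**Working it through.** The plan gives no sample size, power or alpha for this comparison, so there is no figure to reproduce. The check is timing arithmetic.

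**Inputs**
- ELAD course T = 72 to 120 h (SAP 2; Protocol 5.4.3.1.2).
- ELAD start at End of Study Day s. The typical value is s = 2 (SAP 7.3.6); s = 1 and s = 3 are tried as an assumed range.
- Length of Study Day 1, d = 0 to 24 h (Protocol 5.4 says it is under 24 hours).
- Age of the Control baseline sample at randomization, p = 0 to 24 h (Protocol 5.2.3).

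**Formulas, for nominal day D**
- End of Study Day k falls d + 24(k − 1) h after randomization.
- ELAD elapsed time = max(24(D − s), T + 24).
- Control elapsed time = d + 24(D − 1) + p.

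**ELAD, s = 2**
- Day 3: max(24, T + 24) = T + 24. Day 4: max(48, T + 24) = T + 24. The two are identical for every T of 72 h or more.
- T = 72, 96, 120 h gives 96, 120, 144 h after baseline, that is, Study Day 6, 7, 8.
- Day 7: max(120, T + 24) = 120, 120, 144 h.

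The earliest of these samples (Study Day 6) is 72 h after Day 3 and 48 h after Day 4, outside the 24-hour window for both.

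**Both arms, s = 2, with means taking T, d and p as uniform**

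| Nominal day | ELAD range | ELAD mean | Control range | Control mean | Mean gap (ELAD − Control) |
|---|---|---|---|---|---|
| 3 | 96–144 h | 5.0 d | 48–96 h | 3.0 d | +2.0 d |
| 4 | 96–144 h | 5.0 d | 72–120 h | 4.0 d | +1.0 d |
| 7 | 120–144 h | 5.25 d | 144–192 h | 7.0 d | −1.75 d |

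The ELAD mean at Day 7 is 120 h for T up to 96 h and averages 132 h above that: (120 + 132)/2 = 126 h = 5.25 d.

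**Sensitivity**
- If every course lasted 72 h, the ELAD times are 4, 4 and 5 d, and the mean gaps are +1, 0 and −2 d.
- If every course lasted 120 h, the ELAD times are 6, 6 and 6 d, and the mean gaps are +3, +2 and −1 d.
- With s = 1 or s = 3 the shared Day 3 and Day 4 sample falls at Study Day 5–7 or 7–9. One edge case meets the window: s = 1 with T = 72 h gives Study Day 5, exactly 24 h after Day 4.

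**Scale in bilirubin terms.** The documents give no rate of change. At an assumed 2–5% per day in both arms, the mean gaps correspond to 4–10 points of percent change at Day 3 (2 × 2–5) and 2–5 at Day 4. At Day 7 they correspond to 3.5–8.75 in the opposite direction (1.75 × 2–5).

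**Would matched start points alone be enough?** Moving the Control baseline to Study Day 2 gives Control 24 h at Day 3 and 48 h at Day 4, against 96–144 h for ELAD. The gap widens, so the later-of rule is what defeats Days 3 and 4. At Day 7 Control becomes 120 h against 120–144 h for ELAD, which is close.

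**The case against.** The strongest defence is that the rule has a sound clinical reason. Protocol 5.4.1.2 warns that extracorporeal therapy affects bilirubin and prothrombin time, so Lille scores in ELAD subjects need care. That justifies an off-ELAD sample. It does not justify labelling the sample Day 3 or Day 4, or testing it against a true Control Day 3 or Day 4 value.

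Second, each baseline can be read as the start of that arm's assigned treatment, because Control begins immediately after randomization (Protocol 5.4.3.2, SAP 8.2). On that reading the different choice in SAP 7.2.2 does not by itself make this one an error. That is fair, but the section's stated aim is alignment, and at Day 7 its choice leaves the arms about 1.75 days apart.

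Third, the mismatch is not universal. With a start at End of Study Day 2, a subject who stops within 24 h contributes a true Day 4 value. The intervals can also coincide at the extremes, for example 96 h in both arms at Day 3. This stands, but it concerns early stoppers and limiting cases.

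Fourth, the 24-hour window might be meant to override the later-of rule. Then, with the same start, only subjects who stopped within 24 h (Day 3) or 48 h (Day 4) would have an eligible ELAD score. That is a selected group and no better a comparison.

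Two stronger readings are tempting. A reader might infer that the tests will show a false benefit for ELAD. The documents do not support this: the direction depends on whether bilirubin is falling or rising, the daily rate is assumed, and the Lille formula is not given, so no shift across 0.45 can be calculated. A reader might also infer that the survival tables by Lille group are biased between arms. Those tables are presented within treatment group, and no between-arm test is stated for them.

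**Conclusion.** The point holds as a low-impact finding. For ELAD subjects treated for the planned 72 hours or more, the Day 3 and Day 4 scores share one bilirubin value, and the between-arm tests on those days compare unequal windows. Day 7 is also misaligned, in the opposite direction.

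That one late value serves both days follows from the SAP's text and the 72-hour minimum, for any start between End of Study Day 1 and 3. Its placement at Study Day 6 to 8 assumes a start at End of Study Day 2 and an uninterrupted course; interruptions push it later. The mean gaps of about +2, +1 and −1.75 days also rest on uniform timing and vary with course length; at Day 4 the mean gap vanishes if every course stops at 72 hours.

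The Day 3 and Day 4 comparisons cannot support a statement about early response to ELAD. The analysis is exploratory, and neither overall survival nor ECBL20 depends on it. Bilirubin is also compared by visit in SAP 7.3.6.

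**What to change.** In SAP 7.3.5, remove the between-arm chi-squared tests of Lille at Days 3 and 4. Keep those scores as listings, or summarize them for Control only.

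For Day 7, adopt the SAP 7.2.2 start points (pre-ELAD value for ELAD, Study Day 2 value for Control) and its end-point rule. With a start at End of Study Day 2 this gives 120 h for Control. ELAD is 120 h when the Day 7 sample falls more than 6 h after stopping (T below 114 h), and up to 144 h for a full 120-hour course. With starts at End of Study Day 1 or 3, ELAD would be 144 h or 96–144 h, so elapsed time should be reported by arm.

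Requiring one common end visit at least 24 hours after ELAD stops would not work. A full course started at End of Study Day 2 needs a sample at Study Day 8, but Control laboratory tests are daily only to End of Study Day 7 and then resume at Day 14 (Protocol 5.5.1, 5.5.4 and Table 2).

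The cost is a wording change and the loss of the Day 3 and Day 4 between-arm comparisons in the ITT and Safety populations. A small Day 7 difference remains for full courses. No new data are needed. Because the SAP 7.2.2 rules are written for ELAD-treated and Control subjects, the edit should also say which values apply in the ITT analysis to subjects randomized to ELAD but never treated.
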